5.7 Subject Procedure

Subjects will be asked basic demographic and pregnancy status questions. Subjects will be screened for eligibility and no other preparations are required to participate. Following consent, eligible subjects will be fitted with a conventional FHR Monitor while simultaneously undergoing a non-invasive abdominal ultrasound scan using the Vscan Access R2 system with Assisted FHR and a commercially available ultrasound device (reference standard). FHRs will be collected using both devices.

Eight (8) paired ultrasound scans with FHR Monitor determination will be attempted for each subject participating in the study (a total of 16 scans each, 8 with the research device and 8 with the reference device). Each paired scan will last approximately 5 minutes for both determinations, for a total of approximately 40 minutes of total ultrasound exposure. Breaks may be provided between scans based on operator availability or requests by the subject. At least 2 operators will perform scanning for each subject.

A prospective blocked schedule detailing the order in which scanning will be conducted for each operator and subject will be prepared before the start of subject scanning.

Up to 5 clinicians (Experienced sonographers, Novice users e.g. newly qualified sonographers, nurses/midwives, etc.) - with an approximate 80-20 split of novice vs. experienced - with respect to ultrasound familiarity & scanning experience will be aspired for.

The resultant ultrasound and case data (including basic demographics; self-reported pregnancy status; and information about when and how the ultrasound exam was conducted) will be collected for each subject.

All procedures will be conducted at a Sponsor, GE Healthcare (GEHC), facility. All members of the study staff will be qualified based on experience and trained prior to participation.

5.8 Scan Operators

Approximately 5 clinician ultrasound operators may participate in the study at two skill levels:

- **Novice:** Nurse, midwife, medical residents, or technologist with <3 years' experience with obstetric ultrasonography
- **Experienced:** Physicians or technologists with ≥3 years of experience

5.9 Follow-up

No follow-up will be conducted. The subject will be followed for AEs from the time they enter the GE facility to the time they leave the GE facility.

Any data, including images, collected for the subject, up until the time of withdrawal or discontinuation, may still be included in the study results and provided to the Sponsor, unless the subject requests that their data not be used. The site shall document all requests by subjects regarding their data use.

6. STUDY DATA COLLECTION AND ASSESSMENTS

6.6 Primary Assessment

The operator will record FHR values estimated from the reference and research ultrasound devices to the CRF. Relevant demographics and clinical information will also be recorded to the CRF.

6.7 Exploratory Assessments

The device operator will save the ultrasound images, which includes information about the parameter of scanning, for each subject than completes an ultrasound scan in the study. Additional information will be recorded to the CRF as follows:

- Subject ID
- Date of scan
- Duration of scanning
- Patient demographics (age, height, weight, race/ethnicity)
- Gestational age and number, self reported or by LMP or EDD from previous scans
- Trimester (2nd or 3rd)

6.8 Safety Assessments

The description, severity, and device relatedness of any AE or SAE during the study will be recorded. Subjects will, if necessary, be provided with emergency care. In the event of any device issues, the event will be recorded. Safety reporting will be conducted as described in this protocol.

7. QUALIFICATION AND TRAINING PLAN

7.6 Staff Qualifications

All members of the study staff participating in the conduct of the clinical investigation shall be qualified by education, training and/or experience to perform their tasks, and this shall be documented appropriately, as per ISO 14155:2011 for clinical studies.

All members of the study staff participating in the conduct of the investigation shall be qualified by education, training and/or experience to perform their tasks, and this shall be documented appropriately, as per United States Food and Drug Administration (FDA) requirements and ISO 14155:2011.

7.7 Training Plan for the Protocol and Research Device/Product

Before starting the study, the study staff will be trained based on their role in the study on the clinical investigation requirements set forth in this study protocol according to the training plan, as follows:

- *Protocol Training* – All study staff will be trained on the study protocol and, as applicable, on devices. Documentation of such training will be retained at the site as part of the regulatory binder and by the Sponsor as part of the study Clinical History File (CHF).
- *Training objectives* – Objectives will be recorded in each training session.
- *Training logistics* – A qualified trainer authorized by the study Sponsor will conduct training sessions.
- *Target audience* – All site personnel involved with the conduct of the study will be trained on the protocol and, as necessary, on device use.
- *Device Training* – All users will be trained on the VScan Access R2 and Assisted FHR feature per the user manual.

Study staff directly operating or maintaining the research device will be trained based by the Sponsor or qualified based on experience, such as being an imaging scientist, engineer, sonographer, or other medical professional qualified by the site policy.

The Principal Investigator will be ultimately responsible for execution of this study in accordance with the protocol and for device/product use in this study by members of the study staff.

8. SAFETY

The description, severity, and study device relatedness of any AE or SAE during the study will be recorded. Subjects will, if necessary, be provided with emergency care. In the event of any study device issues, the issues will be recorded. Safety reporting will be conducted as described in this protocol.

8.6 Anticipated Adverse Events

FHR determination with ultrasound is widely considered safe for 2nd and 3rd trimester pregnancies without significant comorbidities.^{15, 16, 17} Because no subjects will be enrolled that are in active labor or exhibit significant medical conditions that could pose risk of harm to mother or developing fetus, the risks of this study are expected to be the same as for conventional commercially available ultrasound devices for prenatal scanning.

Diagnostic ultrasound exams involve minimal risk because they use acoustic energy rather than X-rays or other types of ionizing radiation. Ultrasound is commonly used in populations of pregnant women and is not expected to pose additional risks to subjects.^{20, 21} This study enrolls from a population of pregnant women that may foreseeably experience adverse events not related to the study device during the course of this study. In the event that the study staff observed any medical issues that could pose additional risk to the mother or

developing fetus, the subject will be immediately withdrawn and referred for appropriate medical care outside of the study.

Even though manifestation of risks during cardiac, pulmonary, and/or abdominal ultrasound exams is rare, ultrasound can produce effects on the body. Having an ultrasound exam involves some foreseeable risks that are not different from those routinely encountered in routine clinical ultrasound exams, which include:

- Tissue warming
- Discomfort
- Skin irritation
- Bruising
- Abrasions or tears in the skin
- In rare cases, formation of small pockets of gas in body fluids or tissues (cavitation) can occur. The long-term effects of tissue heating and cavitation caused by ultrasound are not known.

As part of this study, subjects will have an ultrasound exam as part of this study that is not required for clinical care. All study scans are completed using non-invasive methods on a commercially available ultrasound device. All exams are performed in a similar manner as routine clinical exams. Thus, study participation is not expected to pose additional risks to subjects beyond those of routine ultrasound scanning.

There is always a chance of unexpected risks. Throughout the study, the Sponsor will evaluate and update safety information in study documents.

8.7 Adverse Event Definitions

Adverse Event (AE): any untoward medical occurrence, unintended disease or injury, or untoward clinical signs (including abnormal laboratory findings) in subjects, users or other persons, whether or not related to the investigational medical device [ISO 14155:2011 3.2]. This includes events related to the investigational device or the comparator and to the procedures involved. For users or other persons, this is restricted to events related to the investigational medical device.

Serious Adverse Event (SAE): an adverse event that led to death; led to a serious deterioration in the health of the subject, that either resulted in a life-threatening illness or injury, a permanent impairment of a body structure or a body function, or in-patient or prolonged hospitalization, or medical or surgical intervention to prevent life-threatening illness or injury or permanent impairment to body structure or a body function; or led to fetal distress, fetal death or a congenital abnormality or birth defect. Planned hospitalization for a pre-existing condition, or a procedure required by the protocol without serious deterioration in health, is not considered a SAE [ISO 14155:2011 3.37].

Adverse Device Effect (ADE): an adverse event related to the use of an investigational medical device [ISO 14155:2011 3.1]. This includes any adverse events resulting from insufficient or inadequate instructions for use, deployment, implantation, installation, or operation, or any malfunction of the investigational medical device. This includes any event that is a result of a user error or intentional misuse of the investigational device [ISO 14155:2011 3.43].

Serious Adverse Device Effect (SADE): an adverse device effect that has resulted in any of the consequences characteristic of a serious adverse event [ISO 14155:2011 3.36].

Device deficiency: an inadequacy of a medical device with respect to its identity, quality, durability, reliability, safety, or performance, such as malfunctions, use errors, and inadequate labelling [ISO 14155:2011 3.15].

Unanticipated serious adverse device effect (USADE): a serious adverse device effect, which by its nature, incidence, severity, or outcome has not been identified in the current version of the risk analysis report [ISO 14155:2011 3.42]. In the United States, any serious adverse effect on health or safety or any life-threatening problem or death caused by, or associated with, a device, if that effect, problem, or death was not previously identified in nature, severity, or degree of incidence in the study documents, will be reported in accordance with 21 CFR §812.3 and applicable laws and regulations.

8.8 Documentation of Safety Events

All adverse events (AE), including all serious adverse events (SAE), are required to be collected, investigated, and documented during the study reporting period, as defined in the study procedure set forth in this protocol. Documentation will include:

- Description of Event
- Date of onset and resolution
- Severity (mild, moderate, or severe)
 - *Mild:* Symptom(s) barely noticeable to the subject or does not make the subject uncomfortable. The AE does not influence performance or functioning. Prescription drugs are not ordinarily needed for relief of symptom(s).
 - *Moderate:* Symptom(s) of a sufficient severity to make the subject uncomfortable. Performance of daily activities is influenced. Treatment of symptom(s) may be needed.
 - *Severe:* Symptom(s) of a sufficient severity to cause the subject severe discomfort. Treatment for symptom(s) may be given.
- Serious (yes/no)
- Causal relationship to investigational medical device? (not related, possibly related, or related)
 - *Not related:* The adverse event is reasonably expected to be related to (or caused by) a concurrent illness, effect of another device/drug or other cause, and is unlikely related to the investigational product.
 - *Possibly related:* The adverse event is reasonably expected to be related to the investigational product, and an alternative etiology is equally or less likely compared to the potential relationship to investigational product.
 - *Related:* There is a strong relationship to investigational product or recurs on re-challenge, and another etiology is unlikely or there is no other reasonable medical explanation for the event.
- Treatment given and/or action taken (procedure stopped, withdrawn from study, or no action)
- Anticipated (yes/no)

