3.2 Study Endpoints

3.2.1 Primary Endpoints:

- FHR data from the investigational and comparator devices on a per-sample basis in bpm (beats per minute)

3.2.2 Exploratory Endpoints:

- The number of subject cases containing scan parameters will be reported and descriptively summarized as necessary to assist in evaluation and optimization of the Vscan Access R2 Ultrasound System.

3.2.3 Safety Endpoints(s):

- Type and number of AEs, SAEs, and device issues.

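### The three causality grades in 8.8 leave no grade for an event with a plausible device role but a likelier alternative cause

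*Combined protocol and SAP*

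**What the plan says.** Section 8.8 requires one of three answers for each adverse event: "Causal relationship to investigational medical device? (not related, possibly related, or related". The definitions that follow are:

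- *Not related*: another cause is reasonably expected, such as "effect of another device/drug or other cause, and is unlikely related to the investigational product".
- The middle grade, *possibly related*, carries two joint conditions: "The adverse event is reasonably expected to be related to the investigational product, and an alternative etiology is equally or less likely" when compared with the device.
- *Related*: "There is a strong relationship to investigational product or recurs on re-challenge, and another etiology is unlikely", or no other reasonable medical explanation exists.

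There is no grade for an unknown or unassessable relationship. Sections 6.8 and 8 require device relatedness to be recorded for any adverse event. Section 8.7 defines an ADE as "an adverse event related to the use of an investigational medical device" and builds the serious and unanticipated serious categories on it, but does not say which 8.8 grades qualify. The safety endpoint in 3.2 is "Type and number of AEs, SAEs, and device issues".

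**The concern.** *Possibly related* is the lowest positive grade, yet it asks for the device to be at least as likely a cause as the alternative. A scale of this kind should give every event a place, and the uncertain events are the ones that most need one. If they have no grade, each assessor must improvise, and the relatedness table then depends partly on how each assessor resolves the gap.

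The uncertain case is easy to foresee here. Under 5.7 a woman is fitted with a conventional fetal heart rate monitor while she is scanned with the research device and with a commercial ultrasound device. Section 8.6 lists non-specific effects such as warming, bruising or irritated skin, and more than one of these sources could produce some of them. It also anticipates events in pregnant women that have nothing to do with the device. Several rival explanations for the same complaint are thus built into the session.

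At stake are the tabulation of relatedness and the device-effect labels in 8.7.

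**Working it through.** The plan gives no figure on this point, and no sample size, power or event rate enters. The check is whether the definitions in 8.8 cover every case.

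Two questions separate the grades: is a device role plausible or unlikely, and is the alternative cause less, equally or more likely than the device? The first condition of *possibly related* is read generously, as met by any plausible device role. A stricter reading would only widen the gap.

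| Device role | Alternative cause | Grade that fits as written |
|---|---|---|
| Unlikely | Reasonably expected | *Not related* |
| Plausible and strong | Unlikely, or no other explanation | *Related* |
| Plausible | Less likely than the device | *Possibly related* |
| Plausible | Equally likely | *Possibly related* |
| Plausible | More likely than the device | None |

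The last row, grade by grade:

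1. *Related* fails. It needs other causes to be unlikely or absent, and here another cause is the leading one.
2. *Possibly related* fails its second condition, which admits an alternative only up to a tie.
3. *Not related* fails its second condition. The event must be one that another cause explains "and is unlikely related to the investigational product", and here the device role is plausible.

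An assessor who must tick a box has two ways out. One is to ignore the bar in *possibly related*. The other is to read less likely than the alternative as if it meant unlikely, and tick *not related*. The second closes the gap, but only by recording a plausible device role as no relationship. The text does not choose between them. The second is the easier step, because the likelier alternative expressly excludes *possibly related*.

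What depends on the grade:

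| Output | Depends on the 8.8 grade? |
|---|---|
| Adverse and serious adverse event totals (3.2) | No |
| Documentation of all adverse events (8.8) | No |
| Serious events to the sponsor within 72 hours (8.9) | No |
| Device issues that could lead to a serious event (8.9, 8.10) | No |
| Tabulation by relatedness | Yes |
| ADE, serious ADE and unanticipated serious ADE labels (8.7) | Probably; no rule links them to the grades |

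On size, the documents give no adverse event rate and no share of events that would fall in the ungraded row, so no expected understatement can be calculated. What can be said is that 10.7 caps enrolment at 25. If all 25 women are counted, one regraded event moves the proportion with a device-related event from 0/25 to 1/25 = 4%, that is, from none to some.

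**The case against.** The strongest reply is that little of the plan's safety reporting rests on this grade. All adverse events are collected and described whatever their cause, serious events reach the sponsor regardless of grade, and device issues are reported separately. An ambiguous event therefore stays visible and can be reviewed again. The study is small and descriptive, with no hypothesis test, and is treated as non-significant risk. All of this stands, and it limits the consequence. It does not give the ungraded event a grade.

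A reader might go further than the text in four ways:

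- *That 8.8 sends these events to* not related. It does not, because that grade also requires an unlikely device role. Recording them there is a likely default, not a written rule.
- *That adverse device effects are under-counted.* The endpoint names no such count and no rule ties the grades to ADE status. Understatement is a plausible direction, not an established result.
- *That every event with a device likelihood below 50% is affected.* This holds only with a single alternative. The comparison is with an alternative cause, so with several the device can be the leading candidate or tie below 50%. If the research scan, the reference scan and the monitor were equally likely, each would stand at 1/3, and a tie still qualifies as *possibly related* when causes are compared one by one. A lower limit for unlikely, such as 10–20%, would be an assumption.
- *That 8.8 contradicts 8.7.* The United States clause there covers unanticipated serious effects "caused by, or associated with, a device". It is broader than the middle grade but applies on its own terms and does not refer to the 8.8 scale. A wide reporting trigger beside a narrower documentation field is not a contradiction.

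It can also be said that a scan is the obvious candidate cause for many local effects, and that ties already count as *possibly related*. That is fair, and it means that the ungraded row may hold few events. The documents do not say how many.

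**Conclusion.** The point holds as a gap in the scale. As written, an event with a plausible device role and a likelier alternative meets none of the three grades. Assessors may record it as *not related* by default, which could understate device-related events and affect the device-effect labels.

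The consequence is modest and confined to relatedness tabulation and labelling. The gap itself rests only on the wording of 8.8. The direction of the effect rests on the assumption that assessors pressed to choose will more often pick *not related*. That is likely from the wording but is not stated. The correction is worth making because relatedness has to be recorded for every adverse event, rival causes are present in each session, and the change is small.

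**What to change.** In 8.8 and on the adverse event form:

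1. Redefine *possibly related* as: *a causal relationship with the investigational device or its use is a reasonable possibility, even if another cause is equally or more likely*.
2. Keep *not related* for events in which a device role is unlikely.
3. State that events graded *possibly related* or *related* count as ADEs, so that the serious and unanticipated serious labels in 8.7 follow from the grade by rule.

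The previously ungraded row then falls under *possibly related*. The third step is needed because rewording the grade alone would still leave its link to ADE status unstated.

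The cost is one definition and one added sentence, with the matching change on the form. The downside is that the number of events reported as *possibly related* may rise slightly, including some that the device did not cause.

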8.9 Reporting of Safety Events and Device Deficiencies/Complaints

The following events are to be reported to the Sponsor within 72 hours of the event occurrence and to the EC per their policy:

- All SAEs and USADEs
- All device issues that could possibly lead to an SAE

Additional follow-up information may be requested by the Sponsor. In addition, safety information may be shared with regulatory agencies and other participating sites, as required by applicable law and regulation.

8.10 Device Deficiencies/Complaints

Device deficiencies/complaints should be reported to the study Sponsor contact identified on the cover page of this protocol. All device deficiencies/complaints will to be collected, fully investigated, and documented in the source document and appropriate case report form (CRF) during the study reporting period. The Principal Investigator is responsible for notifying the Sponsor in the event that there is any device issue that could potentially lead to a SAE.

9. ETHICAL CONDUCT OF THE STUDY

The study will be carried out in accordance with the protocol and with principles enunciated in the current version of the Declaration of Helsinki; the guidelines of Good Clinical Practice (GCP) for medical devices, as set

forth by ISO 14155:2011 and ISO 14971:2010; applicable sections of US FDA 21 Code of Federal Regulations (CFR), and applicable regulatory authority's requirements in the United States.

The study will be conducted and reported in accordance with applicable policies of the governing Ethics Committee (EC) and governing regulatory authorities.

If national or regional EC requirements are less strict than the requirements of GCP, such as ISO 14155:2011 for medical devices, the Sponsor shall make attempts to apply the requirements of this International Standard to the greatest extent possible, irrespective of any lesser requirements, and shall record such efforts.

